Music may have a positive impact on pain and distress for children undergoing intravenous placement. Benefits were also observed for the parents and health care providers.

This study uses similar methods and looked for similar outcomes as Music:Ed, but using recorded rather than live music, and in a non-emergency setting.

The Music:ED study will therefore use a controlled experimental design to investigate the impact of using therapeutic live music in the Alder Hey Paediatric Emergency Department to reduce pain and distress during interventional procedures.

The outcomes of the study will provide evidence for the use of live music in the PED to support and enhance patient experience. Distress is often particularly high within the emergency department. If a patient's experience whilst attending the Emergency Department can be less traumatic, this will be of benefit to all: patients, families and clinicians. A patient who is less distressed is more cooperative and may be easier and quicker to treat.

Methodology and Methods

Research Question

Does live music decrease the pain and distress of patients undergoing a procedure within the paediatric emergency department?

Aims of the Study

Our aims/objectives include:

1. To explore whether live music helps to decrease pain and distress in patients in the Paediatric Emergency Department
2. To explore whether procedures can be carried out with greater ease from a clinician's perspective and whether staff experience of the situation is impacted by the presence of live music.
3. Exploring the overall impact on the ED experience from the patients, families and clinicians' perspectives.

Methodological Approach

We have chosen a mixed method design to provide us with different forms of data and insights from multiple practitioner, parent and patient perspectives throughout the experience.

Quantitative data includes collecting information about the patient's pain levels and qualitative data will be collected from open response questionnaires to explore patient distress and the practitioner, parent and patient perspectives on the experience.

Methods

There will be an experimental (live music) and a control (no live music) group.

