Research Nurses will identify appropriate patients using a screening tool that will outline the inclusion/exclusion criteria. Participant Information Sheets (PIS) will be provided to patients and their families for their appropriate ages. They will be offered a copy of the results if they would like and will be told how the results will be reported when the study is completed.

After gaining written consent from the parent and written or verbal assent from the child, Wong-Baker pain scoring methods will be explained in advance of the procedure. Necessary data will be collected for the CRF.

The participant's involvement in the study will be limited to the length of time of their Emergency Department visit, so will be just one day and one procedure.

For the experimental (music) group, Cascade's musicians will spend eight weeks, twelve hours per week in the ED and will aim to recruit all eligible children during that period. As this is a pilot study recruitment targets need to remain flexible, but are estimated at 60-80 participants (per group).

The same number of participants will be recruited to the control (no live music) group as a comparison, on days that the musicians are not in the department. All patients in both groups will continue to receive standard care. Each child can only be in the study once and for one procedure. Patients will be free to withdraw from the study at any time.

Following the procedure and interviews, patients involved will be offered a sticker and a CD of calming music recorded by Cascade Music as a thank you for their participation. For ethical reasons, this will not be mentioned in advance.

Timeline:

December 2018:

Implementation of study including finalising ethical approval

Recruitment of Research Nurse,

Publicise study within Alder Hey Children's Hospital's Emergency Department.

January - March 2019:

Recruitment of participants to the study, both experimental (music) and control (non-music) groups.

Data collection from participants.

March - May 2019:

Complete data analysis

Write report

Explore dissemination options including publishing and conferences

Plan next funding application

Methods of data collection and analysis

Three sets of data will be collected:

1. Quantitative: Self-reported pain.

A validated observational tool will be used: Wong Baker Faces.

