This is suitable for children age 3+. As children self-report, the Research Nurse will collect this data on a paper CRF. Wong Baker scores will be collected before, during and after the procedure. If mid-procedure collection of pain score is inappropriate, then participants can be asked about mid-procedure pain scores after the procedure.

A self-reported pain score will also be taken in advance, during the recruitment process, to provide a baseline measure.

2. Quantitative: Observed pain.

Data will be collected on observed pain levels using a validated observational tool: Faces, Legs, Activity, Cry and Consolability (FLACC) pain assessment tool.

This tool is suitable and validated for all ages of the recruited participants, from 6 months until 16 years. References regarding justification of this scale for these age ranges are below.^{5 6}

Scoring will take place before, during and after the procedure.

The Research Nurse will carry out this scoring, and when available, an independent observer from the Emergency Department staff will also. The Research Nurse will collect this data on the paper CRF.

Heart rate will also be monitored throughout, where a child is cooperative enough. HR will be noted approximately every two minutes before, during and after procedure, (cleaning marks the beginning of the procedure, final bandage/dressing marks the completion). The Research Nurse will note HR data on the CRF. There will be an option for the Research Nurse to record 'not available' for heart rate measurements either because child refuses or because of probe or monitor issues etc.

3. Qualitative: Distress and experiences of patients, families and clinicians.

Our outcome measures will include collecting qualitative information on patient's distress, and patients', families' and clinician's Emergency Department experience. All recruited patients will receive a paper questionnaire with open text response options.

Qualitative questions for Experimental AND Control Groups:

The following two questions will be asked of both the experimental (live music) AND control (no live music) groups. The questions will be asked of each of these two people: patient and parent/legal guardian.

'Please answer the following questions, in particular, in regard to distress levels/lack of distress':

- Qualitative question 1. What do you think helped you/your child during their procedure?

- Qualitative question 2. Did anything make the situation worse?

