Qualitative questions for Experimental Group Only:

Within the experimental group only, the following three additional questions will be asked, via a paper questionnaire, of each of these three people: patient, parent/legal guardian and clinician. These questions directly link to the objectives of the study.

These questions are in particular regard to music, which is why they would not be appropriate to be asked of the control (no live music) group.

- Qualitative Question 1. How did you feel the music affected the child's distress before, during and after the procedure?

- Qualitative Question 2. Can you tell me about how the live music helped or hindered the procedure?

- Qualitative Question 3. Can you tell me about your experience of the ED (Emergency Department) today, in particular in regard to the music?

The qualitative questions will be included in a open ended questionnaire style sheet which the parent, child or practitioner if the parent wishes, can fill out between the end of the music intervention and when they are discharged from the ward. It will be collected by the RN and stored in a secure room in a locked filing cabinet.

Target population and sampling

This will be a single centre study.

Study participants for both the control and experimental groups of the study will be recruited from AHCH Emergency Department. The study population will consist of children between the age of 6 months and 16 years needing to undergo a painful procedure from a specified list. The Research Nurse will use a screening tool to assess eligibility within this age group.

Necessary data will be collected for the CRF by the Research Nurse:

CRF:

Patient's name

Patient's age

Patient's gender

Parent(s)/legal guardian in attendance during procedure (names)

Whether or not the patient has had this procedure before

How many times the child has visited the hospital in the last 12 months

Have they had an upsetting hospital experience in the past? Yes or no

Record a Wong-Baker pain score at this point (for children age 3+) as a baseline measure

Record whether patient has had analgesia in advance, or during hospital visit

Record use of local anaesthetics e.g EMLA/amecop, LAT gel, cold spray (ethyl chloride)

Record use of Entonox during the procedure

Record if other distraction methods were also used

(Play Specialist/books/bubbles/IPad/TV/ iPhone/ staff dancing and singing, etc)

Record whether the procedure was successful

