Record the duration of the procedure (cleaning marks the beginning of the procedure, final bandage/dressing marks the completion)

Record how many attempts were required to carry out procedure

Record the role and grade of the Clinician carrying out the procedure

Record heart rate at 2-minute intervals if tolerated. Include option for the research nurse to record 'not available' for heart rate measurements either because child refuses or if probe or monitor issues etc

Is there an independent observer present? If so, who?

Inclusion criteria

Parent/Legal Guardian present and able to consent.

Age range: 6 months - 16 years. (see references at end notes 5&6 below)

Procedures: Capillary blood sampling, cannulation, venepuncture, suturing, wound cleaning and closure.

Families and children whose primary language is other than English will be included in the study if their English speaking skills are at a level that they can understand and complete the consent/assent process.

Exclusion criteria

Children with Special Educational Needs, children with global development delay, sensory impairments, neurological deficits or disorders, impairment to pain i.e. spina bifida.

Children in resuscitation or unconscious.

Non-English speaking.

Suspected ingestion of recreational drugs, antidepressants or alcohol

Concerns relating to NAI (non accidental injury)/safeguarding concerns

Life or limb critical injuries

Children too unwell to participate

Recruitment

Research Nurses will identify appropriate patients using a screening tool that will outline the inclusion/exclusion criteria. For inclusion in either group, a parent or legal guardian must be available to give consent, collected by the Research Nurse.

The Research Nurse will introduce the study to potential recruits, and supply and explain Participant Information Sheets. Posters will be displayed within Alder Hey's Emergency Department to promote the study and give some initial details.

The same number of participants will be recruited to the control (no live music) group as a comparison, on days that the musicians are not in the department. All patients in both groups will continue to receive standard care. Each child can only be in the study once and for one procedure. Patients will be free to withdraw from the study at any time.

Ethics and governance

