Full ethics approval will be obtained and clear data protection measures will be put in place for sharing of data between the research team. Parental consent and children's assent will be obtained in all cases. Consent and assent will specifically address the use of quotations in papers, conferences and dissemination.

We do not expect that the study will raise significant issues and will be of minimal risk to the children (and their families). The main issues relate to the engagement of children within research and ensuring that they understand what they are assenting to and are able to indicate (at any point) if they wish to withdraw from the study.

Data Protection

Alder Hey Children's Hospital, as the study sponsor, will own the study data.

The researchers will comply with the requirements of the Data Protection Act. Storage and anonymity: Research nurses will collect data from parents and children and enter them into the database. Data will be anonymised and will be stored electronically on Alder Hey Children's NHS Foundation Trust's secure server. This can be accessed when on trust premises. The data will NOT be shared with other organisations other than members of the study team which includes the University of Liverpool, or exported outside the EU. Consent forms will be kept separately from the data. Information about participants will not be disclosed to anyone. Any identifying information will be changed to maintain anonymity and the data will be stored securely. After storage (10 years), data will be deleted from the AHCFT secure server. Any paper based information such as consent forms will be destroyed.

The researchers will comply with the requirements of the Data Protection Act. This will be achieved through careful and conscientious management of the study including approaching the families, handling the data and through to dissemination of the findings. Only the Research Nurse, PI and treating clinician will access to the child's medical or other records. All data will be encrypted. All electronic files will be encrypted. Reports from and presentations from the study will not contain any quotes directly attributable to individuals and so will be anonymized. Any specific contextual information will be omitted to ensure that participants' identities are not disclosed. This will be made very clear in the information sheet and within the consent/assent forms.

Data Analysis

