Quantitative data will be entered into SPSS. We will analyse the data using the chi-square test for trend, paired samples t-tests and Wilcoxon sign ranks tests as appropriate. Participants with missing data (either before procedure or after procedure) will be excluded from analysis. NVivo 10 Software will be used to assist in the organization and coding of qualitative data (e.g. free text open question responses). Qualitative thematic analysis will be interpretive and iterative. Our approach to synthesizing qualitative and quantitative data will draw on the constant comparative method.

Dissemination

Findings from the study will be disseminated to professionals and to children and their families. Dissemination potentially includes publication in journals and via presentation at conferences and at practice development workshops. This will be done locally through the associated universities and hospitals as well as potentially internationally. By working with colleagues in clinical practice on an on-going basis throughout the study, the researchers anticipate that the study will have a direct impact on practice.

Benefit to patients

Findings will be used to further our understanding of the potential benefits of using live music within the Paediatric Emergency Department, with an aim to improve patient experience.

Link to Alder Hey Research & Universities' Strategies

Alder Hey Children's Hospital's strategy is to build a healthier future for children and young people. One of Alder Hey's main aims is to 'ensure all of our patients and their families have a positive experience whilst in our care'. This study very much follows this ethos, by exploring ways to make the hospital experience a less traumatic one.

A key strength of the University of Liverpool's research strategy is its impact intensive approach. The design of this study will explore ways of making immediate, effective improvements to the care of children and young people.

References:

¹ A. Y. R. Kühlmann(2018) *Meta - analysis evaluating music interventions for anxiety and pain in surgery*. Available at 002 <https://onlinelibrary.wiley.com/doi/abs/10.1/bjs.10853>

² Kari Sand-Jecklin, EdD, MSN, RN, AHN-BC, Howard Emerson, BA, CMP (2010) *The Impact of a Live Therapeutic Music Intervention on Patients' Experience of Pain, Anxiety, and Muscle Tension* *Holist Nurs Pract* 2010;24(1):7–15

³ *J Dev Behav Pediatr.* 2007 Oct;28(5):399-403.

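### Ending the music is not separated from leaving the study, so the missing-score exclusion could drop children who leave because of the music from the pain results

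*Protocol*

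**What the plan says.** Only the protocol is at hand. Four parts of it bear on this point.

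- **Exit.** Methods and Recruitment both state: "Patients will be free to withdraw from the study at any time". Ethics and governance repeats the idea, asking that children "are able to indicate (at any point) if they wish to withdraw from the study". No section mentions ending the music alone, or says whether scores already taken from a withdrawn child are kept.
- **Scoring times.** Under Methods of data collection and analysis, the self-report rule is "Wong Baker scores will be collected before, during and after the procedure" and the observer-rated FLACC rule is "Scoring will take place before, during and after the procedure".
- **Missing data.** Data Analysis states: "Participants with missing data (either before procedure or after procedure) will be excluded from analysis". The rule sits with the quantitative tests.
- **Possible harm.** The music group's patient, parent and clinician are asked: "Can you tell me about how the live music helped or hindered the procedure". Patients and parents in both groups also get an open question on whether anything made matters worse.

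The data items listed under Target population and sampling include other distraction methods and a way to mark heart rate as unavailable when a child refuses. They include no item for music played, refused or stopped early, and none for the reason for withdrawal.

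**The concern.** The exit wording and the exclusion rule are each ordinary. Together they can act on one group only. If a child or family wants the music to end, the only route in the text is to leave the study. If they leave mid-procedure, there is no after score, and the exclusion rule then discards the before and during scores as well.

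Controls hear no music, so they cannot be lost for this reason. A child who leaves because the music was upsetting is also likely to be more distressed than those who stay. That part of the loss is related to the outcome, and it would make the remaining music group look better.

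The protocol calls the study a pilot. The number of children who did not tolerate the intervention is therefore a useful result in itself, and the protocol names no data item that would supply it.

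**Working it through.** **Step 1: follow a child through the text.** The design is "There will be an experimental (live music) and a control (no live music) group". Take a child in the music group:

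| Situation | After score? | Under the exclusion rule |
|---|---|---|
| Dislikes the music, stays, is scored | yes | analysed in the music group |
| Music ended informally, child stays, is scored | yes | analysed in the music group |
| Leaves the study after the last score | yes | analysed, if data are kept |
| Leaves the study before the after score | no | excluded, despite before and during scores |

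Only the last row produces the loss. The trigger is the missing score, not withdrawal as such and not dislike of the music.

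**Step 2: inputs for size.** From the protocol: 60 to 80 children per group, a flexible pilot target. The protocol gives no alpha, power, effect size, SD or withdrawal rate, so there is no stated calculation to reproduce. Assumed for illustration:

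- two-sided 5% test and 80% power;
- a comparison of two group means in SD units (the protocol does not fix the form of the between-group comparison);
- leavers are 2–15% of the music group;
- leavers' scores are g = 0.5 to 2 SD worse than stayers';
- no losses among controls.

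**Step 3: formulas.** If k of n music children leave, the full-group mean equals the stayers' mean plus (k/n) × g. Dropping the leavers therefore moves the music mean in its own favour by

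b = (k/n) × g.

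With no true difference, the chance of a significant result is about

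Φ(b/SE − 1.96) + Φ(−b/SE − 1.96), where SE = √(1/(n−k) + 1/n).

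Example with n = 60, k = 6, g = 2: b = 6/60 × 2 = 0.20; SE = √(1/54 + 1/60) = 0.188; b/SE = 1.066; chance = Φ(−0.894) + Φ(−3.026) = 0.186 + 0.001 = 0.187.

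**Step 4: results.**

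| Leavers (of 60 / of 80) | g (SD) | Shift b (SD) | False-positive rate (60 / 80 per group) |
|---|---|---|---|
| 1 / 2 | 0.5 | 0.008 / 0.013 | 0.050 / 0.051 |
| 3 / 4 | 1 | 0.05 | 0.058 / 0.061 |
| 6 / 8 | 1 | 0.10 | 0.083 / 0.094 |
| 6 / 8 | 2 | 0.20 | 0.187 / 0.234 |
| 9 / 12 | 2 | 0.30 | 0.350 / 0.444 |

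For scale, the difference detectable with 80% power is 0.52 SD at 60 per group and 0.45 SD at 80 per group. A shift of 0.20 SD is 38% (0.20/0.52) to 44% (0.20/0.45) of that; a shift of 0.01 SD is about 2%.

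**The case against.** The strongest reply is that much of this rests on silence.

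- **Withdrawal wording.** It is standard consent language for both groups, not a rule for ending the music. The protocol does not forbid stopping the music and continuing to score, and FLACC needs no self-report. This stands. The text leaves the handling open, so staff may differ.
- **A reader might infer that any child upset by the music is removed.** The text does not support this. A child who stays and is scored remains in the music group, even if the music was ended early. That case adds no bias towards music from exclusion.
- **A reader might infer that harm cannot be reported at all.** The open questions invite exactly such reports, and the exclusion rule sits with the quantitative tests. What remains is that a family that has withdrawn may not complete the form, and free text does not correct a pain comparison.
- **A reader might infer from the CRF list that early stops will leave no trace.** The list is evidently not exhaustive: it omits FLACC and the later Wong-Baker scores, which other text places on the CRF. The fair statement is that no such item is named.
- **Direction.** Distressed controls may also leave. Only the music-related part of the loss is one-sided, and the net direction is not established.
- **Scope.** Reporting of withdrawals is often left to the SAP. But the exclusion rule is stated in this protocol, and an SAP cannot recover scores or reasons that were never collected.

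**Conclusion.** The point holds in a limited form. The protocol does not distinguish ending the music from leaving the study, and its exclusion rule would drop from the quantitative pain results a child who leaves because of the music before the after score. Only the music group can lose children this way, so that component would favour music.

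The size cannot be known from the document. Over the assumed range the shift runs from about 0.01 to 0.30 SD. It becomes material only when about 10% or more leave and their scores are much worse (around 2 SD in the illustration). The leaving rates, the score gap and the test are all assumptions. The document does not support a claim that harmed children as a class disappear from the results. The change is worth making because it is nearly free and the data cannot be recovered later.

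**What to change.** 1. **Data Analysis.** Replace the exclusion of participants with a missing before or after score by analysis of every available score, including during-procedure scores, in the group the child was recruited to. Make this subject to consent for keeping data already collected.
2. **Methods and Recruitment.** State that ending the music is not withdrawal from the study, and that scoring continues unless the family also withdraws from data collection.
3. **CRF.** Add one line: music played, stopped early, and the reason.
4. **Reporting.** Give the number of early stops and withdrawals, with reasons, by group.

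When the music should stop is for the clinical team and is not proposed here.

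The cost is a few sentences and one CRF line. There are two limits. Keeping children with interrupted music may make the music effect look slightly smaller. Children who withdraw fully will still lack an after score, so the change reduces the possible bias but does not remove it.

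### Two of the three named tests are paired and cannot compare music with control; the third could, but is not assigned to do so

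*Protocol*

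**What the plan says.** Under Research Question the protocol asks: "Does live music decrease the pain and distress of patients undergoing a procedure within the paediatric emergency department". Under Methods it sets up the contrast that answers this: "There will be an experimental (live music) and a control (no live music) group". Methods and Recruitment add that controls are enrolled on days without musicians, in equal number and for comparison, and that a child may take part only once. No matching is described. The estimated size is 60 to 80 children per group.

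Wong-Baker (age 3 and over) and FLACC scores are taken before, during and after the procedure. For Wong-Baker there is also an earlier score: "A self-reported pain score will also be taken in advance, during the recruitment process, to provide a baseline measure". For FLACC there may be two raters: "The Research Nurse will carry out this scoring, and when available, an independent observer from the Emergency Department staff will also".

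The quantitative analysis is one sentence under Data Analysis: "We will analyse the data using the chi-square test for trend, paired samples t-tests and Wilcoxon sign ranks tests as appropriate". The next sentence excludes children who lack a value from before or after the procedure.

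**The concern.** Two of the three listed tests need paired values. The pairs in this design are scores on the same child: at two times, or from two FLACC raters. Neither test can set music against control. The trend test can compare two independent groups on an ordered score, but the section gives it no contrast, outcome or time point. The list holds no unpaired test of a mean, a rank or a change.

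The stake is the study's main claim. Under Value of the study the protocol says: "The outcomes of the study will provide evidence for the use of live music in the PED to support and enhance patient experience". If a change within the music arm were taken as that evidence, two errors are open. A change that all children show would be credited to music. And if pain rises in all children and music holds it level, the music arm shows no change and a real effect is missed.

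**Working it through.** **Which test can make which comparison**

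- Paired t-test and Wilcoxon signed-rank: two values on one child. They can describe change within an arm, or compare the two FLACC raters.
- Chi-square test for trend: can compare the two groups on an ordered score, but no such role is stated.
- Unpaired test of a score or a change (two-sample t-test, Mann-Whitney, ANCOVA): none is listed.

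**Inputs for the illustration**

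From the protocol: n = 60 or 80 per group. The protocol gives no basis for that figure, so it can be neither reproduced nor called wrong. Assumed, because the protocol gives none of them: two-sided 5% level, the effect sizes, and a correlation of 0.5 between earlier and later score. At that correlation the SD of the change is SD × √(2 × (1 − 0.5)) = SD, so one unit serves for scores and changes. Scores are treated as continuous.

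**Error 1: shared change, no effect of music**

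The paired t-test in the music arm has noncentrality d√n on n − 1 degrees of freedom. With d = 0.3:

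- n = 60: 0.3 × √60 = 2.324, critical value 2.001, significant in 63% of trials.
- n = 80: 0.3 × √80 = 2.683, critical value 1.990, significant in 76% of trials.

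The range over the assumption is 12% and 14% at d = 0.1, and 97% and 99% at d = 0.5. A two-group comparison has noncentrality 0 here, because the shared change cancels. It rejects in about 5% of trials.

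**Error 2: shared rise of 0.5 SD, music lowers the later score by 0.5 SD**

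Expected change in the music arm is 0.5 − 0.5 = 0, so the paired test is significant in about 5% of trials. A two-group t-test has noncentrality d√(n/2) on 2n − 2 degrees of freedom:

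- n = 60: 0.5 × √30 = 2.739, critical value 1.980, power 78%.
- n = 80: 0.5 × √40 = 3.162, critical value 1.975, power 88%.

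ANCOVA on a baseline that music has not touched cuts the residual variance to 1 − 0.5² = 0.75 of its value. Simulated power is then 88% and 95%.

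Simulation of 20,000 trials per setting agrees with these results. Wong-Baker will have fewer children than n, because it starts at age 3.

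**Adjusted or unadjusted comparison?**

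The groups are formed by day, so this matters for the fix. Take no music effect and a 0.2 SD difference between musician days and other days:

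- Difference in the later score only: unadjusted test rejects in 19% and 24% (n = 60 and 80). ANCOVA works with 0.2/√0.75 = 0.231 SD and rejects in about 24% and 30%.
- Difference in both scores: unadjusted about 19% and 24%. ANCOVA keeps 0.2 − 0.5 × 0.2 = 0.1 SD and rejects in about 10% and 11%. Comparing changes between the arms rejects in about 5%.

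The ranking depends on where the day difference lies. In the other direction, if music had already lowered the earlier score by 0.25 SD and the later one by 0.5 SD, ANCOVA would estimate 0.5 − 0.5 × 0.25 = 0.375 SD instead of 0.5. Neither analysis is safe in every case, so both should be shown.

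**The case against.** The strongest reply is that the plan has a coherent reading: paired tests for change within a child, and the trend test for the comparison of the arms. The sentence leaves the choice among its tests to what suits the data, the control group is recruited for comparison, and a statistical analysis plan that is not shown may assign each test. The study is also a pilot with exploratory aims.

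Much of this stands. A reader might infer that the team will judge music by a p-value within the music arm. The protocol does not say so. The exclusion of children without a before or after value fits a before-to-after analysis but does not prove that one is planned. A reader might also infer that no listed test can compare the groups. That is too strong, because the trend test can.

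A third inference is that music had already changed the score taken before the procedure. The only hint is an open question to the music group: "How did you feel the music affected the child's distress before, during and after the procedure". It asks about perceived distress. The Introduction describes music given during procedures, and nothing states that it starts before the pre-procedure score. This is a reason for a sensitivity analysis, not for dropping adjustment.

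What does not stand is that the freedom to choose cures the list. It permits a choice among three tests, and no unpaired test of a score or change is among them. This is not silence left for a later plan: the protocol names its tests, and two of three do not fit its question. Pilot status does not alter which test can compare two groups.

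**Conclusion.** The point holds as a mismatch between the listed tests and the question, and it should be fixed. Two of the three tests cannot compare music with control, and the one that could has no assigned role. This conclusion rests on the design alone and needs no assumed number.

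The harm is conditional on a within-arm result being read as the effect of music. In that case, at an assumed two-sided 5% level and 60 or 80 per group, a shared change of 0.3 SD gives a significant music-arm result in 63% or 76% of trials without any effect. A 0.5 SD effect that offsets an equal rise is found in about 5%, where a two-group comparison finds it in 78% or 88%. These sizes move with the assumed effects.

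A reader might also infer that a two-group test would settle whether music works. It would not: children are allocated by day, and differences between musician days and other days remain under any of these analyses.

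**What to change.** Rewrite the Data Analysis paragraph to say the following.

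- During- and after-procedure Wong-Baker (age 3 and over) and FLACC scores are compared directly between music and control, with the difference and its 95% confidence interval.
- Wong-Baker: ANCOVA adjusted for the recruitment score, which is already collected.
- FLACC: comparison adjusted for the pre-procedure score, with the unadjusted comparison as a sensitivity analysis in case music had begun before that score. A Mann-Whitney test or an ordinal model serves as a check for skewed scores.
- If the trend test is kept, it compares the arms, on a named score.
- Paired tests only describe change within an arm or compare the two FLACC raters.
- The exclusion for a missing score before the procedure does not apply to the unadjusted comparison, which does not use that score.
- Confounding by musician days remains and limits what the comparison can show.

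The cost is the rewording of one paragraph and a little more analysis. No extra patients or measurements are needed.
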